7.4 Evaluation at Completion of Study Intervention

7.4.1 Study Visit 3

The final study visit will occur 6 months (\pm 1 month) after initiation of the intervention. Participants will be told to fast for 8 hours before the study visit. Fasting instructions will be provided to participants prior to their study visit, and participants will receive a phone call reminder the day before the visit to fast overnight. The following procedures will be performed during this visit:

1. Review medical history, medications, and laboratory test results
2. Physical exam including measurement of weight and symptom assessment
3. Vital signs assessment: blood pressure, heart rate, respiratory rate, and oral temperature
4. ECOG performance status
5. Pregnancy test for women of child-bearing potential. Women who have had a hysterectomy, both ovaries removed, or a tubal ligation will not be required to have a pregnancy test.
6. Blood collection for clinical labs (approximately 10 mL). Laboratory blood tests will be done for a Complete Blood Count and Automated Differential (CBDF), a Complete Metabolic Panel (CMPL), a Lipid Panel, and hemoglobin A1C to monitor for potential adverse effects of the intervention and to confirm that laboratory levels meet the eligibility requirements for continuation in the trial (See Appendix A). If lab results within 30 days prior to this visit for any of these tests are available in the medical record, the blood test(s) will not be done.
7. Blood collection for research purposes (26 mL): 6 mL will be collected for measurement of protocol-specific biomarkers (serum concentrations of cytokines, chemokines, and adhesion molecules), and 20 mL will be banked for DNA extraction and future studies.
8. Fecal specimen for measurement of fecal elastase. A stool collection kit and instructions will be provided to the participant before the scheduled visit. The specimen will be self-collected at home. The participant will receive a phone call reminder the day before the visit to collect the fecal specimen and bring it to the study visit.
9. Interviewer-administered follow-up questionnaire to obtain information about changes in exposures and behaviors since the baseline visit, and to assess alcohol use and surgical procedures that will impact the risk of recurrent pancreatitis
10. Self-administered QLQ-C30 and QLQ-PAN28(CP) to assess quality of life and pain level
11. Collect study agent and diary
12. Assess compliance (pill count)
13. Review study diary
14. Assess adverse events
15. Endoscopic pancreatic function test (ePFT) and simultaneous endoscopic ultrasound (EUS) and fasting pancreatic fluid to measure secretin-stimulated peak bicarbonate concentration; inflammatory cytokines, chemokines, and adhesion molecules

7.5 Post-intervention Follow-up Period

Clinical research staff will make follow-up telephone calls to study participants on days 30 ± 7 , 60 ± 7 , and 90 ± 7 after completion of Study Visit 3 to assess symptoms and adverse events.

7.6 Methods for Clinical Procedures

Endoscopic pancreatic function test (ePFT) and simultaneous endoscopic ultrasound (EUS) and fasting pancreatic fluid. Patients will be instructed to fast overnight (8 hours) before the endoscopic testing. Instructions regarding preparing for the ePFT and the simultaneous EUS will be provided to the participants before each study measurement at Screen 2 and Study Visit 3 (6 months).

Fecal specimen. A stool collection kit and instructions regarding the collection of the fecal specimen will be provided to participants prior to their study visit. The fecal specimen will be self-collected at home and brought to the study visit. Participants will receive a phone call reminder the day before the visit to collect the fecal specimen and bring it to the study visit. The fecal specimen will be processed as specified in the Laboratory Manual and stored at -80°C.

Blood specimen. A blood specimen (approximately 10 mL) will be collected from each participant at the Screen 2 visit for blood tests to confirm eligibility. A Complete Blood Count (CBC) and a Comprehensive Metabolic Panel (CMPL) will be done to confirm that laboratory levels for acceptable organ, hepatic, and renal function are within the eligibility requirements. See Appendix A for Clinical Laboratory Minimum Test Requirements. If a patient's lab results within 35 days before the Screen 2 visit are available in the medical record and are within eligibility range, their blood will not be drawn at the Screen 2 visit. Otherwise, the patient's blood will be drawn to confirm eligibility.

Approximately 36 mL of blood will be collected from each participant at Study Visits 1, 2, and 3 using a standard phlebotomy protocol. Fasting instructions will be provided to participants prior to their study visit, and participants will receive a phone call reminder the day before the visit to fast overnight (8 hours). The date and time of the blood draw and of the participant's last meal will be recorded.

Approximately 10 mL of blood will be drawn for laboratory blood tests to monitor for potential adverse effects of the intervention and to confirm that laboratory levels meet the eligibility requirements for continuation in the trial. A fasting Lipid Panel will be done at all study visits. A CBDF and a CMPL will

be done at Study Visits 2 and 3. Fasting hemoglobin A1C will be measured at Study Visits 1 and 3. Creatine phosphokinase (CPK) will be measured at Study Visit 1. See Appendix A for Clinical Laboratory Minimum Test Requirements.

The CMPL and CBDF test results will be utilized to screen for any issues that could be related to an adverse event or affect eligibility for the trial. CBDF and CMPL lab results from the Screen 2 eligibility visit will be used to establish patient-specific references prior to initiation of therapy. If blood tests were not done at the Screen 2 visit for a CBDF and CMPL; and lab results within 30 days prior to Study Visit 1 for these tests are not available in the medical record, a CBDF and CMPL will be done at Study Visit 1. The Lipid Panel includes tests for cholesterol, high density lipoprotein cholesterol, low density lipoprotein cholesterol, and triglycerides. Since the study agent is a cholesterol lowering agent, we feel that it is important to establish baseline lipid levels prior to initiating the study agent (Study Visit 1) and to monitor lipids at subsequent study visits. Hemoglobin A1C is used to assess glucose control in insulin-dependent diabetics whose glucose levels are very labile and in whom single blood glucose measurements may not accurately reflect the level of control present over the preceding few weeks. Glucose and hemoglobin A1C will be used to establish a baseline (Study Visit 1) for monitoring adverse events (incident diabetes) during the trial. CPK will be tested to establish a baseline for monitoring myopathy, a rare complication associated with the study agent (<1%). CPK will be measured at Study Visit 1 to establish a patient-specific reference for this indicator of muscle toxicity. If the participant reports unexplained muscle pain or weakness during the trial, CPK will be tested again to check for elevation.

Twenty-six mL of blood will be collected for research purposes. Six mL of blood will be drawn into a red top serum vacutainer tube for measurement of protocol-specific biomarkers (cytokines, chemokines, and adhesion molecules). Twenty mL of blood will be drawn into three vacutainer tubes, including one 6 mL red top serum tube and two 7 mL lavender top EDTA tubes, for DNA extraction and use in future studies. The blood will be collected and processed as specified in the Laboratory Manual. Processed specimens will be stored at -80°C.

Biomarkers. Pancreatic fluid will be analyzed for secretin-stimulated peak bicarbonate levels. Study assays for blood and pancreatic fluid concentrations of cytokines, chemokines, and adhesion molecules will be performed in [name] laboratory at CSMC. Inflammatory cytokines will be measured in pancreatic fluid collected 30 minutes after secretin stimulation and in serum samples collected at each visit using our Luminex-based MAGPIX multiplexing analysis system in [name] lab using methods previously described [36].

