2. BACKGROUND

2.1 Study Disease

Pancreatic cancer is the fourth leading cause of cancer death in the US, and it has an extremely high fatality rate [1]. The incidence for pancreatic cancer in the US has been increasing for more than a decade, in parallel with the rates of pancreatitis, and both are driven by the epidemic of obesity and diabetes [2]. Chronic pancreatitis (CP) is a progressive inflammatory disease of the pancreas, characterized by chronic pancreatic inflammation and scarring, irreversibly damaging the pancreas and resulting in loss of exocrine and endocrine function. The primary symptoms of CP are abdominal pain, maldigestion, and steatorrhea [3]. Chronic pancreatitis, which results from repeated episodes of acute pancreatitis, is the strongest identified risk factor for pancreatic cancer and increases the risk by at least 13.3 fold [4]. Pancreatitis and pancreatic cancer exist in a disease continuum; patients with an episode of acute pancreatitis have a 20-30% likelihood of one or more recurrent episodes, with progression to chronic pancreatitis in an estimated 10% of the recurrent cases [2, 5, 6]. Interventions that have the ability to prevent the development of pancreatic cancer in this high-risk population would therefore address a currently unmet major public health problem and would have a high clinical impact. Despite this need, and the associated high impact potential, few studies have investigated the effectiveness of a chemopreventive strategy for pancreatic cancer.

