6.2 Reported Adverse Events and Potential Risks

The most common (incidence $\geq 5.0\%$ patients) reported adverse events (AEs) are upper respiratory infection, headache, abdominal pain, constipation, and nausea. Other AEs reported in clinical trials ($<5\%$) were diarrhea, rash, dyspepsia, flatulence, and asthenia.

Persistent increases in serum transaminases (to more than 3 x ULN) have occurred in approximately 1% of patients who received simvastatin in clinical studies. When drug treatment was interrupted or discontinued in these patients, the transaminase levels usually fell slowly to pretreatment levels. The increases were not associated with jaundice or other clinical signs or symptoms. It is recommended that liver function tests be performed before the initiation of treatment, and thereafter when clinically indicated.

Simvastatin occasionally causes myopathy manifested as muscle pain, tenderness or weakness with creatine kinase above 10 x ULN. Myopathy sometimes takes the form of rhabdomyolysis with or without acute renal failure secondary to myoglobinuria, and rare fatalities have occurred. Predisposing factors for myopathy include advanced age (≥ 65 years), female gender, uncontrolled hypothyroidism, and renal impairment. The risk of myopathy, including rhabdomyolysis, is dose related. The risk of myopathy and rhabdomyolysis is increased by high levels of statin activity in plasma. Simvastatin is metabolized by the cytochrome P450 isoform 3A4 (CYP3A4). Certain drugs which inhibit this metabolic pathway can raise the plasma levels of simvastatin and may increase the risk of myopathy. These include itraconazole, ketoconazole, posaconazole, voriconazole, the macrolide antibiotics erythromycin and clarithromycin, and the ketolide antibiotic telithromycin, HIV protease inhibitors, boceprevir, telaprevir, the antidepressant nefazodone, cobicistat-containing products, or grapefruit products. Combination of these drugs with simvastatin is contraindicated. If short-term treatment with strong CYP3A4 inhibitors is unavoidable, therapy with simvastatin must be suspended during the course of treatment.

Increases in HbA1c and fasting serum glucose levels have been reported with HMG-CoA reductase inhibitors, including simvastatin.

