11. REPORTING ADVERSE EVENTS

DEFINITION: AE means any untoward medical occurrence associated with the use of a drug in humans, whether or not considered drug related. An AE can therefore be any unfavorable and unintended sign), symptom, or disease temporally associated with participation in a study, whether or not related to that participation. This includes all deaths that occur while a participant is on a study.

Please note that all abnormal clinical laboratory values that are determined to be of clinical significance based on a physician's assessment are to be reported as AEs. Those labs determined to be of no clinical significance or of unknown clinical significance (per the physician's assessment) should not be reported as AEs. Any lab value of unknown clinical significance should continue to be investigated/followed-up further for a final determination, if possible.

A list of AEs that have occurred or might occur can be found in §6.2 Reported Adverse Events and Potential Risks, as well as the Investigator Brochure or package insert.

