13.7 Evaluation of Toxicity

All participants will be evaluable for toxicity from the time of their first dose of simvastatin.

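### HbA1c is measured at Visits 1 and 3 to watch for incident diabetes, but no by-arm analysis of its change is planned, so a modest simvastatin effect could go unreported

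*Combined protocol and SAP*

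**What the plan says.** Section 6.2 names the effect: "Increases in HbA1c and fasting serum glucose levels have been reported with HMG-CoA reductase inhibitors, including simvastatin". It gives no size or rate.

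Section 7.6 sets the schedule ("Fasting hemoglobin A1C will be measured at Study Visits 1 and 3") and the purpose ("Glucose and hemoglobin A1C will be used to establish a baseline (Study Visit 1) for monitoring adverse events (incident diabetes) during the trial"). The schedule of events in 7.1 and Appendix A agree on the two visits.

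Section 11 governs what happens to a laboratory value. On one side, "all abnormal clinical laboratory values that are determined to be of clinical significance based on a physician's assessment are to be reported as AEs". On the other, "Those labs determined to be of no clinical significance or of unknown clinical significance (per the physician's assessment) should not be reported as AEs". No HbA1c or glucose threshold is attached to either rule.

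Section 13.7, on toxicity, is a single sentence beginning "All participants will be evaluable for toxicity". Section 13.5 plans descriptive statistics, graphics and random-effects trends for the secondary variables. HbA1c is not a secondary endpoint in 1.2 or 8.2.

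**The concern.** The protocol names a metabolic effect of the study drug and schedules a paired measurement in both arms that could estimate it. It then plans no analysis that uses the pair. The stated route turns each HbA1c value into a yes-or-no judgement made one patient at a time. That route can pick up a clear new case of diabetes. It is poorly suited to a small average rise, because each value may look unremarkable and none need be recorded. The trial studies a preventive drug in patients whose disease can itself impair endocrine function, so a by-arm estimate of the glycaemic effect is worth having even when it is imprecise.

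**Working it through.** **1. The plan's own figure.** The documents give no figure for HbA1c, glucose or diabetes. Their one power calculation is for peak bicarbonate (13.1 and Table 3): 16 versus 8, difference 15 mEq/L, SD 13, one-sided alpha 0.05, power 82%. A noncentral t calculation with d = 15/13 = 1.15 gives 82.5%, which reproduces it. It neither supports nor weakens this point.

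**2. Where the HbA1c values go.**
- Collected: Visits 1 and 3, both arms (7.1, 7.6, Appendix A).
- Endpoint list: absent from 1.2, 8.1 and 8.2.
- 13.4: bicarbonate only.
- 13.5: secondary variables. The preliminary cross-sectional statistics profile the population and are not an analysis of change by arm.
- 13.7: evaluability only, with no laboratory summary and no comparison of arms.
- Section 11: an AE if a physician judges the value clinically significant.

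The last is the only stated route from the laboratory value to a result.

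**3. What an AE count can show.** Let p be the chance that a simvastatin participant has a recorded glycaemic AE. The documents do not give p, so a range is assumed. The chance of no recorded event is (1 − p)^n, with n = 20 (all randomised to simvastatin) or n = 16 (after the planned 20% dropout).

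| Assumed p | n = 20 | n = 16 |
|---|---|---|
| 1% | 82% | 85% |
| 2% | 67% | 72% |
| 5% | 36% | 44% |
| 10% | 12% | 19% |
| 20% | 1% | 3% |

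Zero is the likelier result only when p is below 1 − 0.5^(1/n), which is 3.4% for n = 20 and 4.2% for n = 16. If zero were seen, the one-sided 95% upper limit, 1 − 0.05^(1/n), would be 13.9% for 0/20 and 17.1% for 0/16. A zero count would therefore say little.

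**4. What a by-arm comparison can show.** At 16 versus 8, the standard error of the difference in change is SD × √(1/16 + 1/8) = 0.433 SD. With t(0.975, 22 df) = 2.074, the 95% half-width is 2.074 × 0.433 = 0.90 SD. The documents give no SD for HbA1c change. For assumed SDs of 0.30, 0.45 and 0.60 percentage points the half-width is 0.27, 0.40 and 0.54 points. Two-sided 5% power is about 14% for a true shift of 0.4 SD, 26% for 0.6 SD and 60% for 1.0 SD.

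**5. Who would have a Visit 3 value.** Under 8.3, the end-of-study visit for participants who permanently stop the agent omits the clinical laboratory draw and the follow-up questionnaire. Chart results are still reviewed, but a Visit 3 HbA1c is not planned for them.

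**The case against.** The case on the other side is that the trial is small and preliminary, that diabetes is captured elsewhere, and that a comparison of this size would be too imprecise to matter. Much of this stands.

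- **Other sources exist.** Appendix F asks at Visit 3 about newly diagnosed diabetes (item 4g) and diabetes drugs (items 6a to 6g), the concomitant-medication form records indication, and the metabolic panel with glucose is repeated at Visits 2 and 3. These can reveal incident diabetes or raised glucose. However, no by-arm analysis of them is planned either, and the diagnosis and drug items cannot show a mean HbA1c shift.
- **Values of unknown significance are not simply dropped.** Section 11 asks that they be followed to a final determination where possible. A value finally judged not significant still goes unreported as an AE.
- **Monitoring.** Section 12.4 refers to a monitoring plan held on file and to committee review. The plan cannot be seen here, and safety monitoring would not replace a stated analysis of results.

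Four stronger readings are tempting, and the documents support none of them.

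- A reader might infer that a real effect would usually be reported as zero. That depends on p, which is not given. Assume a non-diabetic HbA1c mean of 5.5 to 5.7%, SD 0.35 to 0.40, a rise of 0.2 points and an AE only above 6.5%: the chance of no event among 16 then runs from 33% to 84%. The plan does not set that threshold, and diabetes is not an exclusion.
- A reader might infer from section 2.1, where the disease is described as "irreversibly damaging the pancreas and resulting in loss of exocrine and endocrine function", that the AE route fails because one patient's rise cannot be attributed to drug or disease. Section 11.1 records AEs regardless of relatedness, with a treatment assignment code, so they can be counted by arm without individual attribution.
- A reader might infer that the HbA1c comparison would bound the harm. At a half-width of 0.90 SD it cannot exclude a modest effect.
- A reader might see an error in calling the glucose baseline a Visit 1 value. Section 3 assigns baseline glucose to Screen 2, and 7.6 makes the Screen 2 panel the pre-treatment reference. This is wording only.

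**Conclusion.** The point holds as a cheap improvement to the analysis plan. HbA1c is collected for a risk the protocol names, no by-arm analysis of its change is specified, and the only stated route for the values is a physician-judged AE without a threshold. A modest drug effect could therefore go unreported. This follows from the text and needs no outside figure.

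The probability of its going unreported cannot be stated, because the documents give neither the effect size nor the AE probability. The gain from the fix is limited: an estimate whose 95% half-width is about 0.90 SD of the change, assuming that 16 and 8 participants have both values and that the SD is the same in each arm. Missing Visit 3 values, or a split by diabetes status, would widen it further. The documents do not say how many participants will have diabetes at baseline.

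**What to change.** Add to section 13.7:

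1. HbA1c at Visits 1 and 3 by arm, with the between-arm difference in Visit 3 HbA1c adjusted for Visit 1 and its 95% interval. Label it as estimation and not a test. Show it separately for participants with and without diabetes at baseline (Appendix E, item C3), since changes in diabetes treatment would otherwise blur the drug effect.
2. A by-arm count of incident diabetes among those without diabetes at baseline. Define it by a laboratory threshold that the sponsor fixes in advance and applies to the recorded value, together with the new-diagnosis and diabetes-drug items of Appendix F. It should not depend on the clinical-significance judgement in section 11.
3. The number in each arm lacking a Visit 3 HbA1c, with the reason, because 8.3 omits the clinical laboratory draw and the follow-up questionnaire for those who permanently stop the agent.

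The cost is a few lines of text and one small table from data already scheduled. It needs no new blood draw or visit and changes nothing in patient management. The downside is a wide interval, which must not be read as evidence of no effect.

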8. CRITERIA FOR EVALUATION AND ENDPOINT DEFINITION

The overall objective of this trial is to examine the effect of simvastatin use versus placebo at 6 months from baseline (Study Visit 1) on pancreatic function and inflammatory mediators in patients with recurrent acute pancreatitis (at least two episodes of acute pancreatitis in the past 12 months). Participants will be on the study drug from Study Visit 1 until the last study visit (Study Visit 3 at 6 months) when the final endoscopic procedure will be performed. Primary and secondary endpoints are measured in specimen samples taken after 8 hours of fasting.

8.1 Primary Endpoint

Primary: To measure changes in pancreas exocrine function (secretin-stimulated peak bicarbonate concentration in the pancreatic fluid) as measured by the endoscopic pancreatic function test (ePFT). We hypothesize that participants randomized to simvastatin will experience a greater increase from baseline in peak bicarbonate concentration measured at 6 months from baseline compared to the placebo group.

8.2 Secondary Endpoints

8.2.1 To measure changes in endoscopic ultrasound score (EUS), a measure of pancreatitis. We hypothesize that compared to the placebo group participants randomized to simvastatin will experience a greater reduction from baseline in EUS score.

8.2.2 To measure changes in serum and pancreatic secretions of the following targets: interleukins (IL; 1 α , 1 β , 1RA, 2, 4, 5, 6, 7, 8, 9, 10, 12p40, 12p70, 13, 15, 17A, 17F, 18, 21, 22, 27, 23, 31), BDNF, CD40L, EGF, ENA78, Eotaxin, FASL, FGF β , GCSF, GMCSF, GROA, HGF, ICAM1, IFN α , IFN β , IFN γ , IP10, LIF, Leptin, MCP1, MCP3, MCSF, MIG, MIP1 α , MIP1 β , PDGF β , PIGF1, NGF, Rantes, Resistin, PAI1, SCF, SDF1 α , TGF α , TGF β , TNF α , TNF β , TRAIL, VCAM1, VEGF, VEGFD. . We hypothesize that participants randomized to simvastatin will experience a greater decrease in pro-inflammatory markers and a greater increase in anti-inflammatory markers.

8.2.3 To assess changes in pancreatitis-related readmissions. We hypothesize that participants randomized to simvastatin will experience fewer episodes of pancreatitis-related readmissions. A pancreatitis-related readmission will be defined as a hospital readmission that is due to complications from the previous pancreatitis episode, as determined by a physician; or an independent episode of acute pancreatitis defined by at least two of the following 1) Typical upper abdominal pain; 2) Elevation in serum amylase or lipase ≥ 3 times ULN; 3) Features of acute pancreatitis on cross-sectional imaging. Source documents include: 1) lipase or amylase levels; 2) physician notes; 3) imaging results.

8.2.4 To assess changes in quality of life measures using the QLQ-C30 and QLQ-PAN28(CP). We hypothesize that participants randomized to simvastatin will experience improvement in quality of life scores.

